15.7. Handling of Missing Data

Missing data will be assumed to be missing at random. No data will be imputed.

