5.4.4. Rationale for Control Group

The use of a randomized placebo control group added to established standard of care provides the best scientific evidence of efficacy and safety. The use of a placebo control provides a concurrent comparator group, accounting for not only a placebo effect but continued standard of care. The use of a placebo control is critical to assess the safety and tolerability of OCA but also as a comparator for the high rate of clinical events which are expected in this advanced population.

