7.4.3. Clinical Criteria for Monitoring for Potential Hepatic Decompensation

Patients will be monitored for potential hepatic decompensation events throughout the study. Clinical criteria for monitoring these events and the interruption/discontinuation of investigational product is summarized in [Table 4](#).

Investigational product should be discontinued permanently if the patient received a liver transplant or experiences multi-organ failure as defined in Table 4, Part A. Patients should continue to return for scheduled study visits for safety follow-up.

Patients who experience other potential hepatic decompensation events defined in Table 4, Part B should be closely monitored until normalization or stabilization. Patients may be rechallenged after a minimum of 30 days if fully resolved OR stable and approved by the Medical Monitor and Investigator.

Table 4: Clinical Criteria for Monitoring Potential Hepatic Decompensation Events and Interruption / Discontinuation of Investigational Product

Hepatic Decompensation Events Requiring Mandatory Discontinuation of Investigational Product	
Decompensation Event	Action Taken / Rechallenging Criteria
Liver Transplant Multi-organ failure requiring hospitalization	Discontinue IP permanently and follow patients until normalization/stabilization. Continue to return for scheduled study visits for safety follow up.
Hepatic Decompensation Events Requiring Interruption of Investigational Product	

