8.4. Dose Adjustment, Interruption, and Withdrawal from Investigational Product or Study

Investigational product may be temporarily decreased (eg, from 10 mg twice weekly to 5 mg twice weekly, or from 5 mg twice weekly to 5 mg once weekly) or temporarily or permanently stopped based on tolerability concerns. Investigational product may be resumed at the maintenance dose upon resolution of gastroenteritis or worsening renal function or dehydration if there is no evidence of liver injury. For rechallenge following all other dose interruptions (see Table 5), investigational product should be initiated at a lower dose and patients monitored more frequently with up-titration considered based on tolerability.

Adjustments, interruptions, discontinuation, and any rechallenge of investigational product should be implemented per the criteria outlined in Table 5. Patients that discontinue investigational product are expected to continue in the study (and follow the regular visit schedule, with the exception of PK sampling [trough PK may be required in the event of an AE consistent with hepatic injury or decompensation]) until the end of the study, but may withdraw consent at any time.

Table 5: Criteria for Dose Adjustment, Interruption, Discontinuation, and Rechallenge

DOSE ADJUSTMENT		
Criteria	Action Taken with IP	Adjustment
New Onset Severe Pruritus	Drug holiday or less frequent dosing	Return to original dose regimen if tolerated
DOSE INTERRUPTION		
Criteria	Action Taken with IP^a	Rechallenge^b
If liver biochemistries indicative of suspected hepatic injury are identified as exceeding upper threshold criteria and require immediate interruption (see Part A of Table 3) ^c	Interrupt immediately upon initial observation	Patient may be rechallenged after a minimum of 30 days if fully resolved OR stable and approved by the Medical Monitor and Investigator.
Other liver biochemistries indicative of suspected hepatic injury are outside upper threshold criteria upon repeat testing as defined in Part A of Table 3 ^d	Interrupt after confirmation by repeat testing	
Liver biochemistries indicative of potential hepatic decompensation in the absence of symptoms (see Part B of Table 3) ^e	Closely monitor until normalization or stabilization. If values continue to increase relative to the baseline value, interrupt	

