15.1. Analysis Populations

The following patient populations will be evaluated and used for presentation and analysis of the data:

- The Intent-to-Treat (ITT) Population will include all randomized patients who receive any amount of investigational product (OCA or placebo). The ITT Population will be the primary population used for summarizing efficacy assessments.
- The Safety Population will include all patients who received at least one dose of investigational product (placebo or OCA). The Safety Population will be the primary population used for safety analyses.
- The PK population will include all patients receiving OCA who have adequate concentration-time profiles to characterize OCA and its conjugates and must not have any major protocol deviations that potentially affect exposure levels.

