15.5. Efficacy Analyses

This study does not plan to test a formal hypothesis for any efficacy endpoint.

The endpoints of efficacy assessments are change in total and direct bilirubin, INR, creatinine, albumin, platelets, ALP, ALT, AST, and GGT from baseline to Week 48 (end of the study), change from baseline to Week 48 in CP score and components of the CP score, and change from baseline to Week 48 in MELD and components of the MELD score. Analyses of change from Baseline to Week 48 (end of study) will be modelled between treatment groups using ANCOVA model with change from Baseline as the dependent variable, treatment group and randomization stratification factor as fixed effects and the baseline value as a covariate. The same analysis will be carried out using percentage change from Baseline as the dependent variable.

Analyses of change from Baseline to Week 48 (end of study) will be modelled between treatment groups using ANCOVA model with change from Baseline as the dependent variable, treatment group and randomization stratification factor as fixed effects and the baseline value as a covariate. The same analysis will be carried out using percentage change from Baseline as the dependent variable.

Summary statistics of the laboratory values will be provided by treatment group. The results, change from Baseline, and percentage change from Baseline values, as well as estimates of least-square (LS) means, standard errors (StdErr), and 2-sided 95% CIs, will be presented by treatment group. Estimates of the mean difference between treatment groups, the StdErr of the difference, and 2-sided 95% CI of the difference will also be presented.

Risk Scores: Changes from baseline in the MELD score and in CP score, C4, FGF-19 and plasma bile acids will be summarized and analyzed using the Wilcoxon Rank Sum Test. The median differences and 95% CI of the median differences between treatment groups will be

constructed using Hodges-Lehmann estimate. If the median differences between treatments are not symmetrical around the median, the Sign Test may be used.

Shifts in MELD scores from Baseline will be reported by visit using the following categories: <10, 10 to <12, 12 to <13, 13 to <14, 14 to <15, and ≥ 15 .

CP class will be presented in shift tables showing the shift from baseline to each scheduled post-baseline visit by the count and percentage of patients within each shift classification.

Individual factors will be presented in a listing.

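### Week 48 laboratory, MELD and CP comparisons treat values lost to death as missing at random and have no rule for post-transplant values, so they can shift toward the arm with more liver failure

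*Protocol*

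**What the plan says.** Section 15.7 contains the protocol's entire missing-data rule: "Missing data will be assumed to be missing at random. No data will be imputed". It does not mention death or transplant.

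Section 15.5 sets the main comparison: "Analyses of change from Baseline to Week 48 (end of study) will be modelled between treatment groups using ANCOVA model", with arm, randomisation stratum and baseline as the only other terms. It covers bilirubin, INR, creatinine, albumin, platelets, ALP, ALT, AST, GGT, CP and MELD. MELD and CP, with C4 and FGF-19, also get a rank comparison in the sentence ending "plasma bile acids will be summarized and analyzed using the Wilcoxon Rank Sum Test", with a Hodges-Lehmann estimate.

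Section 15.1 builds ITT from every randomised patient who took study product, and adds: "The ITT Population will be the primary population used for summarizing efficacy assessments".

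Section 7.4.3, on liver transplant and multi-organ failure, stops product permanently and continues: "Patients should continue to return for scheduled study visits for safety follow-up". Tables 4 and 5 repeat this. Section 8.4 says the same of stopping product in general: "Patients that discontinue investigational product are expected to continue in the study".

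Section 5.4.4 justifies the placebo arm partly "as a comparator for the high rate of clinical events which are expected in this advanced population".

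**The concern.** There are two separate problems.

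**Death.** A laboratory value after death does not exist, so calling it missing at random gives it no sensible meaning. Where death follows liver failure, its absence is also tied to the quantity being analysed. The chosen model does not even exploit the stated assumption. An ANCOVA on Week 48 completers is safe only if absence depends on nothing beyond arm, stratum and baseline. Under missing at random, absence may also depend on values seen at earlier visits, and this model never uses those values.

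**Transplant.** A transplanted patient who attends Week 48 is observed, not missing. The difficulty there is which value is used: bilirubin, INR, MELD and CP then describe a new liver, yet would be scored as improvement from baseline. Section 14.1.2 notes that MELD is used in organ allocation, so transplant is linked to the endpoint.

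Section 5.4.1 says the trial will evaluate whether OCA can stabilise bilirubin. A contrast that moves toward the arm with more liver failure would mislead on that question.

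**Working it through.** **1. The plan's own figure.** Section 15.2 adds 20 OCA + 10 placebo for PK and 20 more for safety and efficacy: 20 + 10 + 20 = 50, or 25 per arm at 1:1. This reproduces the stated total. The protocol gives no death or transplant rates and no expected Week 48 values. Every rate and laboratory value in steps 3 to 5 is therefore an assumption.

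**2. What each patient contributes at Week 48 as written.**

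| Patient | Contribution to the ANCOVA |
|---|---|
| Alive, no transplant, attends | Own value |
| Dies before Week 48 | None; earlier visits not used |
| Transplanted, attends | Post-transplant value (inferred: no rule removes it) |
| Transplanted, does not attend | None |

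Table 1 schedules chemistry and coagulation at Weeks 3, 6, 12, 18, 24, 30, 36 and 42 before Week 48, so the unused data exist.

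**3. Closed form for mean bilirubin change.** Assume no drug effect, a change of +0.3 mg/dL in patients without failure, and -2.5 mg/dL after transplant. With death rate d and transplant rate t, the observed arm mean is

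[(1 - d - t) × 0.3 + t × (-2.5)] / (1 - d).

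- Placebo, d = 8%, t = 4%: (0.264 - 0.100) / 0.92 = 0.178.
- OCA, extra deaths only, d = 20%, t = 4%: (0.228 - 0.100) / 0.80 = 0.160. Difference -0.02.
- OCA, extra transplants only, d = 8%, t = 12%: (0.240 - 0.300) / 0.92 = -0.065. Difference -0.24.
- OCA, both, d = 20%, t = 12%: (0.204 - 0.300) / 0.80 = -0.120. Difference -0.30.

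Negative means that OCA looks better.

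**4. Simulation.** 4,000 trials per scenario, 25 per arm, 20% CP-C, with the protocol's ANCOVA terms. Patients who fail tend to be those deteriorating fastest. Baseline bilirubin has a median of 3 mg/dL in CP-B, and post-transplant bilirubin a median of 0.8 mg/dL. The drug changes only the failure rates. Placebo is held at 8% death and 4% transplant.

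| OCA death / transplant | ANCOVA as written (mg/dL) | Trials favouring OCA | Post-transplant values also dropped (mg/dL) | P(OCA worse), ranks as written | P(OCA worse), death and transplant ranked worst |
|---|---|---|---|---|---|
| 8% / 4% | 0.00 | 50% | 0.00 | 0.50 | 0.50 |
| 16% / 4% | -0.10 | 60% | -0.08 | 0.47 | 0.52 |
| 8% / 12% | -0.35 | 78% | -0.09 | 0.43 | 0.52 |
| 16% / 12% | -0.45 | 83% | -0.17 | 0.41 | 0.54 |
| 24% / 12% | -0.58 | 89% | -0.26 | 0.37 | 0.57 |

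The two rank columns give the chance that an OCA patient's bilirubin change is worse than a placebo patient's (0.50 = no difference). In every unequal scenario the ANCOVA and the ranks as written favour the arm with more failure. Dropping post-transplant values shrinks the shift without removing it. Ranking the events worst reverses the direction.

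**5. Sensitivity to one patient.** One transplant taking MELD from 20 to 8, among 20 observed patients, moves an arm mean by (8 - 20) / 20 = -0.6 points. This applies to means and does not carry over to the Hodges-Lehmann estimate.

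**The case against.** Much of the case on the other side stands.

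- **Events are compared elsewhere.** Section 15.6 plans log-rank, Kaplan-Meier and Cox comparisons by arm for death, liver-related death, transplant and a first-event composite. Transplant and a persistent 3-point MELD rise are adverse events of special interest, summarised by arm under Section 15.4.1. All deaths are adjudicated (Section 15.9), and the DMC meets about quarterly (Section 15.8). A reader might infer that the Week 48 tables are the only between-arm efficacy comparisons, or that hepatic harm would be hidden. The protocol supports neither.
- **Use of post-transplant values is inferred.** The post-transplant visits are described as safety follow-up, and ITT selects patients, not values. A SAP not available here could exclude them.
- **MELD and CP are not analysed by means alone.** The rank analysis and the shift tables by visit would show some deterioration before an event.
- **Deaths alone do little** in the closed form (-0.02 mg/dL). Larger shifts need transplants, or deaths concentrated in the fastest decliners.
- **Week 48 mapping.** Table 1 puts Week 48 in one column with the early-termination and end-of-treatment visits. A reader might infer that those values become Week 48 values, but no rule says so.
- **Status.** PK and safety are the primary objectives, and Section 15 rules out formal hypothesis testing.

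None of this rescues the blanket wording of Section 15.7 or the single-visit model in Section 15.5. Both are stated rules, not details left open, and a SAP that handled death properly would have to depart from them.

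**Conclusion.** The concern holds for the Week 48 laboratory, MELD and CP contrasts. If death or transplant differs by arm, these can shift toward the arm with more failure. Under the assumed rates the bilirubin shift ran from -0.02 to -0.30 mg/dL in the closed form and from -0.10 to -0.58 mg/dL in the simulation. With equal failure it was zero. Transplants drive the larger shifts, and that part depends on post-transplant values actually being analysed. Deaths matter mainly if those who die were declining faster, which is plausible for liver death but is not stated in the protocol. The direction held in every unequal scenario tried; the size is only illustrative.

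The documents do not support the stronger claim that harm would go unseen, because the events are reported by arm. With secondary, untested endpoints, this should be fixed before analysis but is not a must-fix.

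**What to change.** 1. **Section 15.7:** limit missing-at-random to data missing for reasons other than death or transplant.
2. **Section 15.5:** exclude post-transplant values from change-from-baseline analyses.
3. **Section 15.5, liver tests:** replace the Week-48-only ANCOVA with a repeated-measures model on scheduled visits already collected (treatment by visit, baseline by visit, CP class). All nine post-baseline laboratory visits would need 9 × 10 / 2 = 45 unstructured covariance terms from about 50 patients. A prespecified subset such as Weeks 12, 24, 36 and 48 needs 4 × 5 / 2 = 10. State that this model does not by itself resolve death.
4. **Section 15.5, MELD, CP and bilirubin:** supplement the planned Wilcoxon analysis (newly applied to bilirubin) with a version that ranks death worst and transplant next worst. Step 4 of the working shows that item 2 alone is not enough.
5. **Section 15.5 and synopsis:** delete the end-of-study gloss after Week 48, since double-blind treatment continues beyond it (Section 7.1.3).

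The cost is protocol and SAP wording, with no new data. The small downside is that the ranked analysis measures a composite outcome rather than the score or laboratory value alone. Placing transplant next to death is also a judgement, since Section 14.1.2 notes that the threshold for transplant listing varies by region.

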15.8. Data Monitoring Committee

An independent DMC includes hepatologists, pharmaceutical physicians, epidemiology/cardiology expert(s), and statistician(s) not involved in the study as Investigators, adjudication committee members, or consultants. The DMC will have oversight of the study conduct as defined by the DMC charter. All members will have considerable experience with clinical study conduct and DMCs. Any candidate found to have a conflict of interest or whose name is listed on the Food and Drug Administration (FDA) debarment list will not be offered membership. Conflicts of interest will be assessed regularly, and if members are found to have a new conflict of interest they will be replaced.

The DMC will meet approximately quarterly at scheduled meetings and ad hoc meetings will be convened, as appropriate, to review safety and efficacy data in order to ensure the safe and proper treatment of patients. Based on review of these data, the DMC will advise the Sponsor on the validity and scientific merit of continuing the study.

Written minutes of both the open and closed DMC sessions will be prepared. The closed minutes will be made available to the appointed Sponsor representatives only after the database is locked.

Data listings provided to the DMC do not contain individual patient treatment information; however, the DMC will have access to the database and may unblind individual patient data as appropriate. Summary tables reviewed by the DMC during closed sessions will include an overall column containing information regarding all patients and separate treatment columns with 'dummy' labels, ie, the actual treatment groups are used, but are not identified. Data reviewed during the meetings will include, at a minimum, disposition, demographics, exposure, clinical laboratory results, MedDRA-coded AEs, and AEs leading to early withdrawal of investigational product. At each meeting, detailed narratives of interval SAEs (including events resulting in death) are reviewed by the DMC in addition to a cumulative list of all SAEs.

The DMC may agree to adjust meeting frequency based upon actual and projected safety and efficacy data availability. Adjustments to or stopping of the protocol defined doses may be considered based on DMC evaluation of OCA safety and tolerability.

All Investigators and responsible IRBs/IECs will be informed of any decisions made by the Sponsor based on recommendations from the DMC relating to patient safety, which alter the conduct of this study. The Investigators will inform the patients of such actions and the protocol, PIS, and ICF will be revised, as appropriate.

15.9. Adjudication Committees

All suspected liver-related clinical events, major adverse cardiovascular events (MACE)/expanded MACE, and drug-related hepatic injury events that occur after administration of the first dose of investigational product will be reviewed by the following blinded adjudication committees, depending on event type, before inclusion in any analysis. The 3 committees and event types they are responsible for adjudicating are as follows:

- Cardiovascular Adjudication Committee (CAC): Adjudicates all suspected MACE, including all deaths
- Hepatic Outcomes Committee: Adjudicates all deaths and suspected liver-related outcomes
- Hepatic Safety Committee: Adjudicates all suspected drug-related hepatic injury events

Each adjudication committee will have a charter that documents the reporting of events by the study site, definition of the suspected events to be adjudicated, supply of source documentation to the committee, entire data flow and process from committee membership, review of the events by the committee, reporting of the final assessment, and the working procedures of the committee.

The adjudication committee members will include experts with relevant adjudication experience; they will not be involved in the study as Investigators, DMC members, or consultants. Any candidate found to have a conflict or whose name is listed on the FDA debarment list is not offered membership. Conflicts of interest are assessed regularly, and if members are found to have a new conflict of interest they will be replaced.

The adjudication of suspected events will be based on available source documentation, including but not limited to individual clinical study data, hospital records, histology, discharge summaries, and/or death certificates. The adjudication committees will not receive any individual patient treatment or site-specific information. The assessment of events will be conducted in compliance with study-specific procedures, manuals, GCP, and all other applicable regulatory requirements, including the archiving of essential documents.

16. DIRECT ACCESS TO SOURCE DATA/DOCUMENTS

16.1. Study Monitoring

Study records at each site will be monitored at regular intervals by a representative of the Sponsor, the CRA. The role of the CRA is to aid the Investigator in the maintenance and documentation of complete, accurate, legible, well organized and easily retrievable data. In addition, the CRA will ensure the Investigator's understanding of all applicable regulations concerning the clinical evaluation of the investigational product and will ensure an understanding of the protocol, reporting responsibilities and the validity of the data. This will include ensuring that full and appropriate essential documentation is available.

In order to perform this role, the CRA must perform source data verification and as such must be given access to the patient's primary source documentation (eg, paper or electronic medical records such as consent to participate in the study, visit dates, screening and randomization numbers, demographic information, medical history, disease history, physical examination, vital signs, laboratory assessments [copy of laboratory reports], AEs, concomitant medications, dates of dispensing investigational product, ECGs, etc) that support data entries in the eCRF. The eCRF must be completed promptly after each visit to allow the progress and results of the study to be closely followed by the Medical Monitor.

The Investigator may exercise judgment in allowing the CRA access to particular sections of the patient's medical records if these are deemed irrelevant to the performance, observations or conduct of this study.

16.2. Audits and Inspections

The Investigator should understand that it may be necessary for the Sponsor, the IEC/IRB, and/or regulatory agencies to conduct one or more site audits during or after the study and agrees to allow access to all study-related documentation and information and be available for discussion about the study.

